If suspicion of an unacceptable risk, including serious health threat to subjects, arises during the clinical investigation, or when so instructed by the TSC / DMEC or regulatory authorities, the sponsor shall suspend the clinical investigation while the risk is assessed. The sponsor shall terminate the clinical investigation if an unacceptable risk which cannot be controlled is confirmed. The sponsor shall consider terminating or suspending the participation of a particular investigation site or investigator in the clinical investigation if monitoring or auditing identifies serious or repeated deviations on the part of an investigator. If suspension or premature termination occurs, the terminating party shall justify its decision in writing and promptly inform the other parties with whom they are in direct communication. If, for any reason, the sponsor shall inform the responsible regulatory authority as appropriate and ensure that the TSC / DMEC is notified, either by the Chief Investigator or by the sponsor. If the suspension or premature termination was in the interest of safety the sponsor shall inform all other principal investigators.

Access to or breaking the blinding code in the case of suspension or premature termination would be decided by the independent DMEC.

END OF TRIAL

The end of trial is defined by the last visit and completion of data collection of the last participant undergoing the trial, which will be August 2025. The sponsor, or delegated individual in the study team must notify the NIHR and HRA of the end of a clinical trial within 90 days of its completion.

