MRC	Medical Research Council
NHS	National Health Service
NICE	National Institute for Health and Care Excellence
NIHR	National Institute for Health and Care Research
PPI	Patient and Public Involvement
PSR	Psychiatric Status Ratings
RA	Research Assistant
RCT	Randomised Controlled Trial
REC	Research Ethics Committee
REDCap	Research Electronic Data Capture
RfPB	Research for Patient Benefit
SCID	Structured Clinical Interview for DSM-IV
SAE	Serious Adverse Events
SES	Standardised Effect Size
SOP	Standard Operating Procedures
SU	Service User
SURG	Service User Reference Group
TAU	Treatment As Usual
TFA	Theoretical Framework of Acceptability
TMF	Trial Master File
TMG	Trial Management Group
TSC	Trial Steering Committee
WHOQOL	World Health Organisation Quality of Life
YMHRU	Youth Mental Health Research Unit

iii. TRIAL SUMMARY

Trial Title	Cognitive behavioural therapy in comparison to treatment as usual in young adults at high risk of developing bipolar disorder (Bipolar At Risk): A randomised controlled trial to investigate the efficacy of a treatment approach targeted at key appraisal change (BART II)
Internal ref. no. (or short title)	(BART II)
Trial Design	Our trial will be a multicentre, rater -blinded randomised control trial (RCT) with 2 parallel arms. It will compare a psychological intervention (Cognitive Behavioural Therapy for Bipolar At Risk (CBT _{BAR})) + Treatment As Usual (TAU) (treatment condition) to TAU alone (control condition).
	Outcome and mediational variables will be collected at baseline, 17-weeks, 27-weeks (after therapy cessation), and at 52-weeks.
	The primary outcome is mood swing symptom severity assessed by SCID-5 + Psychiatric Status Ratings/PSR's (SCID Longitudinal Follow-Up Evaluation (LIFE)) [1] at 27-week (post treatment) as measured by the PSR scores as an average of the prior 4 weeks. A longitudinal severity rating of overall symptom levels for each week over the time period (prior 4 weeks) is completed providing two LIFE scores, one for mania and one for depression [1].
	Up to 26 individual weekly therapy sessions of up to 60 mins will be offered within a 26-week treatment window. Participants will be randomised to one of two trial arms. Randomisation will be independent and concealed, using permuted stratified blocks where site (5-levels) and BAR group (3-levels) are the stratification factors. It will be conducted via a web-based system conducted within York Clinical Trials Unit (CTU).

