The leaflets and posters will have the contact details for who to contact in the research team when making a referral. When a referral is made, the member of the research team will conduct a brief screening check and check verbal consent to contact. Full details about the process for accepting referrals, making initial contact with a referred participant, and conducting the baseline assessment are explained in more detail in the Research Assistant Manual.

Eligibility will be confirmed with the assessor who conducted the baseline assessment and with a member of the research team based at the central site (Manchester) or with the local site lead or PI. The outcome will be recorded on an eligibility review form entered on REDCap (Research Electronic Data Capture).

CONSENT

Verbal consent to contact will be sought by a relevant professional involved in the potential participant's care (e.g. GP, university counsellor). To aid this initial discussion, all potential participants will be provided with access to the study materials described above (leaflet, animation, etc). Prior to taking written, informed consent, all potential participants will be provided with a Participant Information Sheet. This will be either given in person to the potential participant by the relevant professional involved in their care, e-mailed, or sent to them in the post. Participants will be in receipt of the PIS for at least 24 hours prior to providing written, informed consent.

Written, informed consent will be taken in person at a face-to-face appointment with the research assistant. However, in the event there are restrictions in place that prevent a face-to-face appointment (e.g. COVID-19 related restrictions) we will utilise existing approaches to taking consent remotely (approved by the sponsor including audio recording the consent appointment) and obtaining written consent when it is possible to meet face-to-face. Audio recording will be done in line with the sites NHS policy and procedures. Audio recording of consent will follow the sites local NHS Trust policies and procedures. Audio recordings will be transferred to a secure NHS drive and will only be accessible by members of the research team with delegated responsibility to access, as per the study delegation log.

**Please refer to the BART II Participant Flow Diagram found in Appendices (#1)

PAYMENT

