Participants will receive a £20 payment upon completion of the baseline and each follow-up appointment at 17-, 27-, and 52-weeks (£80 in total). In addition, a 39-week check in phone call will be conducted with each participant to confirm that contact details remain the same.

THE RANDOMISATION SCHEME

Eligibility will be confirmed via completion of the eligibility review form following the baseline assessment. This will be completed at an eligibility supervision between the research assistant and a supervisor (central site supervisor e.g. CI or trial manager, or local site lead or PI with delegated responsibility). The outcome of the eligibility review form will then need to be entered onto REDCap within 2 working days of completion of the review. If the person is eligible, randomisation will be undertaken automatically once entered in REDCap. Participants will be randomised to one of two trial arms (CBT_{BAR} + TAU **or** TAU alone). Randomisation will be independent and concealed, using permuted stratified blocks (using site and BAR Group*), via a web-based system at York Clinical Trials Unit.

*Confirmed BAR Group will be based on hierarchical rule system. Group 1 will be the stratification grouping for any participants meeting Group 1 and another BAR group (e.g. meets criteria for BAR Group 1 and 2). Group 2 will be the stratification grouping for any participants that meet BAR Group 2 and 3).

METHOD OF IMPLEMENTING THE RANDOMISATION/ALLOCATION SEQUENCE

The allocation is made known to the trial manager (to monitor adherence to the randomisation algorithm), the local trial administrator, local PI or site lead, and local trial therapist(s) by email and SMS text message. The allocation is made known to the participant by letter from the local trial administrator. Blinding of the allocation code will be maintained for research assistants.

BLINDING

Single blind – assessors will be blind to treatment condition. Blindness will be maintained using a wide range of measures which we have implemented successfully in other single blind trials within our trust research departments. These include separate offices for the therapists and research assistants, protocols for answering telephones including reminders for clinicians, participants and family members about the blind, protocols for message taking and secretarial support, separate diaries and pigeon holes and data file security, using passwords and encryption of randomisation information.

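### The protocol lets people who are told earlier allocations confirm eligibility, so with permuted blocks the next allocation can be guessed better than chance by someone admitting participants

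*Protocol*

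**What the plan says.** Two places in Section 5 of the protocol say who confirms eligibility. Under Recruitment & Participant Identification, the person who did the baseline assessment does so jointly "with a member of the research team based at the central site (Manchester) or with the local site lead or PI". Under The Randomisation Scheme, the review form is completed by the research assistant and a supervisor, described as "central site supervisor e.g. CI or trial manager, or local site lead or PI with delegated responsibility". The outcome must be entered in REDCap within 2 working days, and entry of an eligible participant triggers randomisation automatically.

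The next subsection, on implementing the allocation sequence, lists who is told the result. One recipient is the trial manager, whose stated reason for being told is to check that the algorithm is followed. The others are "the local trial administrator, local PI or site lead, and local trial therapist(s) by email and SMS text message". For the assessors, "Blinding of the allocation code will be maintained for research assistants". The Chief Investigator is not on the notification list.

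The sequence is held in a web system at the CTU, "using permuted stratified blocks where site (5-levels) and BAR group (3-levels) are the stratification factors" (Trial Summary). It is described as independent and concealed. No block length is given. BAR group for stratification follows a fixed hierarchy: Group 1 takes precedence over 2, and 2 over 3.

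**The concern.** Two roles appear on both lists: the trial manager, and the local PI or site lead. A person in either role may decide whether the next participant enters while holding the allocation history of that participant's stratum.

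A secure web system stops anyone from reading the list. It does not stop prediction from past assignments, because each permuted block must balance. If recent allocations in a stratum have favoured one arm, the other is more likely to come next.

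Some entry criteria in Section 4 call for judgement: help seeking, need for inpatient or acute psychiatric care, primary substance abuse, and the medication exclusion where at-risk status cannot be confirmed. An expectation about the next arm could sway a borderline call on these. The resulting imbalance could lie in unmeasured prognosis. The primary ANCOVA (Section 8) adjusts for site, BAR group, baseline depression and mania PSRs and prior CBT, and would not fully remove it. Section 5 protects the outcome assessors' blinding in detail but has no matching safeguard at entry.

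**Working it through.** **Who is on which list**

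| Role | May confirm eligibility | Told allocations |
|---|---|---|
| Chief Investigator | yes | not listed |
| Trial manager | yes | yes, no site restriction stated |
| Local PI or site lead | yes | yes, worded as local |
| Research assistant | yes, jointly | no |
| Local administrator, therapists | not named | yes |

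The overlap is therefore in the text. It is one of several permitted routes, not the only one.

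**Strata.** The protocol states no figure for predictability. Its own related figure is about 68 participants per site, and 338/5 = 67.6 reproduces it. There are 5 × 3 = 15 strata, averaging 338/15 = 22.5 participants.

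**Fixed blocks (assumed lengths).** Take a complete block of length 2m and an observer who knows all earlier allocations in the stratum and always guesses the arm that is behind.

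Share guessed correctly = [m + (4^m / C(2m,m) − 1)/2] / (2m). Share certain before assignment = 1/(m + 1).

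- Length 4 (m = 2): [2 + (16/6 − 1)/2]/4 = 2.83/4 = 70.8%; certain 1/3 = 33%.
- Length 6 (m = 3): [3 + (64/20 − 1)/2]/6 = 4.10/6 = 68.3%; certain 1/4 = 25%.
- Length 8 (m = 4): [4 + (256/70 − 1)/2]/8 = 5.33/8 = 66.6%; certain 1/5 = 20%.

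Simulating 338 allocations over 15 strata, so that the last block of a stratum may be incomplete, lowers these to about 70%, 67% and 65% guessed, and 30%, 21% and 16% certain (strata of 22 to 23). Unequal strata (about 40, 22 and 6 per site) change little.

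**Randomly varied blocks (assumed sets).** In the same simulation the observer also knows which lengths are possible.

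| Lengths | Guessed correctly | Certain |
|---|---|---|
| 2/4 | 72% | 10% |
| 4/6 | 68% | 6% |
| 2/4/6 | 70% | 4% |
| 4/6/8 | 67% | 2% |

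Varying the lengths removes most of the certainty but hardly lowers the guess rate. For a supervisor who has not seen earlier allocations the rate is 50% and nothing is certain, whatever the block length.

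**Scope for timing.** The green recruitment target in Table 1 is 2.2 per site per month. Split evenly over three BAR groups (assumption), that is 2.2/3 = 0.73 per stratum per month. With about 21 working days in a month (assumption), the expected number of other entrants to the same stratum in a 2-working-day window is 0.73 × 2/21 = 0.07. Delaying entry would rarely change the arm.

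**The case against.** The sequence is held by the CTU and released only after eligibility is entered, so calling it concealed is not false. The overlap is optional, and sign-off by the Chief Investigator is already available. Local leads learn only their own site's allocations. Every review is joint with a research assistant who is kept blind. Recruitment procedures also commit to documenting enquiries, referrals and randomisations by team to capture sources of bias. Withholding block length from a document that sites read is good practice. The guess rates are ceilings, since they assume perfect tracking of a stratum.

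All of that stands, and it rules out several stronger readings that a reader might infer:

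- *That the last allocation of each block is known.* This needs fixed blocks of known length; the protocol gives none.
- *That the supervisor can choose the stratum.* BAR group follows a fixed hierarchy on operational criteria. Control by the supervisor would be an inference.
- *That the 2-day window lets someone steer the arm.* At the planned recruitment rate it gives little leverage, and the text does not say who enters the form.
- *That 15 strata make each allocation more predictable.* What matters is that the stratum and its history are known.
- *That block sizes ought to be stated.* Their absence is missing detail, not an error.

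The objection does not remove the rule itself: two roles told of allocations may confirm eligibility, and even varied blocks leave them well above 50%.

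**Conclusion.** The point holds in a limited form. As written, Section 5 allows the trial manager, or the local site lead or PI, to confirm eligibility while knowing earlier allocations in the stratum. Such a person could guess the next arm correctly about 67% to 72% of the time, against 50%. This rests on assumed block lengths (fixed at 4 to 8, or varied within 2 to 8) and on full knowledge of the stratum's history. It also takes the trial manager to be told of all sites, since no restriction is stated. If the trial manager who is notified were the CTU's and not the lead site's, the overlap for local leads would remain.

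What is exposed is the borderline eligibility decision. A reader might go on to infer that concealment has failed or that the 0.5-point target effect would be biased. The document supports neither: it describes a vulnerability, and no size of bias in the treatment effect is shown. This is a cheap improvement to make, not a flaw that undermines the design.

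**What to change.** Amend both eligibility statements in Section 5 (Recruitment & Participant Identification, and The Randomisation Scheme) so that the supervisor who confirms eligibility and BAR group with the blinded research assistant is someone not notified of that site's allocations. The Chief Investigator fits, being already a permitted supervisor and not on the notification list. The Chief Investigator does review blind breaks, but those reveal isolated allocations and not the running history of a stratum. Another site's lead would also serve.

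The notification list can stay as it is. Removing the trial manager from it would conflict with duties the protocol gives that role: monitoring the randomisation algorithm, arranging the alliance measure for therapy participants, and overseeing the interviews with treated participants.

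The cost is a change to the eligibility delegation and slightly more central coordination of sign-off. No new staff, data or analysis are needed.

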6. TRIAL TREATMENTS

TREATMENT CONDITION (CBT_{BAR} + TAU)

The CBT_{BAR} approach will utilise the manual used and refined in our RfPB trial. The treatment manual utilises a Cognitive Behavioural Therapy (CBT) treatment with a number of permissible interventions. An empirically tested cognitive model is required in order to derive effective treatments: this is achieved by developing an idiosyncratic formulation based on a specific cognitive model of mood swings (ICM) [57] determining treatment strategies and techniques targeting key appraisal change and coping behaviours. The ICM model used for formulation proposes that people hold a range of extreme and contradictory beliefs concerning their mood and other internal states (e.g. energy levels). For example, believing that being highly active is both the key to their success and a sign of
losing control of their mind. Owing to these beliefs, a person engages in recurrent cycles of feeling, thinking and behaviour that maintain and escalate current mood states. The therapy helps clients to identify these maintenance factors that are proposed to make their mood a problem, to learn to tolerate and accept common changes in mood, and to build up their quality of life in ways that are independent of mood state given that such attempts to control mood often get in the way of living their life goals.

The ICM model used to derive treatment targets is underpinned with empirical support from a range of research studies within clinical and non-clinical samples [57]. Studies indicate the acceptability and significant positive impact on bipolar symptoms and functioning of the therapy for people with BD [85-87]. There is also support for this model being applicable in patients with cyclothymia [88]. The model was considered appropriate for young people at risk of BD given the evidence that these appraisals are prospectively associated with bipolar symptoms, are also associated with risk or cognitive vulnerability factors for the development of BD [89], with poorer social and occupational functioning [87, 90] and distinguish BD from unipolar depression [91].

The CBT_{BAR} manual describes overarching principles of every treatment session; a positive therapeutic relationship, person centred practice and active listening and validation of experiences (taken from core principles for CBTp, [92]) and normalising and education of mood swings. Each session is delivered within the CBT model where core aspects are observed: agenda setting, review of home task, agreement on treatment goals, monitoring of target appraisals and behaviours and a new home task set. A range of permissible interventions are delivered within a 26-week treatment envelope allowing up to 26 sessions as follows:

- Mood continuum work
- Problem list generation
- Goal setting
- Idiosyncratic formulation derived from model
- In session measurement of appraisals and behaviour
- Cognitive strategies to target key appraisals of mood: advantages / disadvantages; developing alternative explanations; evidential analysis; surveys
- Behavioural strategies: behavioural experiments; behavioural analysis including intended mood management

Using this CBT_{BAR} manual in our feasibility trial showed positive results on our primary outcome of feasibility and acceptability. Inspection of the data showed that Retention to the allocated intervention was high, more specifically 32 of the 37 participants (86%) who were allocated to the CBT_{BAR} received an adequate dose (≥ 6 sessions) of treatment. Of the 5 participants (14%) who did not receive the dose threshold, the range of sessions attended was between 1-5 sessions. All participants met for at least 1 session. Total session numbers ranged between 1 and 26 across all participants and a grand total of 523 sessions were attended by all participants within the trial. An average of 14 sessions was attended across participants allocated to CBT_{BAR}. Although not powered to test difference between groups results indicated participants in the CBT_{BAR} arm significantly improved compared to those who received TAU alone across measures of symptoms (depressed mood) and functioning at 27-weeks with gains maintained at the 52-week follow-up. Analysis showed that risk of conversion to mania/hypomania was reduced for those randomly allocated to CBT versus TAU, although this did not reach statistical significance but it was not powered to do so (OR 27-week: 0.53, 95% CI: 0.11, 2.45, p= 0.42; OR 52-week: 0.40, 95% CI: 0.11, 1.49, p= 0.17).

The intervention will be delivered by trained psychological therapists (Senior Clinical Psychologists or Psychological Therapists) with experience of working with young adults with mental health problems, to ensure competence in engaging this population and delivering the intervention to a high standard. Trial therapists will receive training in delivering CBT_{BAR} by the study team (three days training, with two-day booster sessions in subsequent years). Additionally, therapists will make use of recording-based supervision (at a minimum frequency of each fortnight) to aid learning and practice as well as adherence to the treatment manual.

Fidelity to the treatment protocol will be assessed by rating audio recordings of therapy sessions using the Cognitive Therapy Scale - Revised (23). This is a widely-accepted approach to the standardisation of CBT, which we have used successfully in previous large-scale trials. All therapists in participating centres will be trained initially, and therapy supervision will be provided by means of regular meetings. All sessions will be taped with the patient's consent (participants may be asked to listen to the tapes as part of their homework) and a random sample of tapes (stratified for stage of therapy) will be rated in order to monitor fidelity and assist supervision; this will be done throughout the lifetime of the trial to provide some quality assurance and ensure corrective action can be taken if required. Following each session, therapists will complete a session record that monitors content of sessions in terms of agenda targets, homework tasks and change strategies used, which is another strategy we have used in previous trials; thus, fidelity can be used as a process variable in analyses.

CONTROL CONDITION (TAU ALONE)

The control condition is treatment as usual plus follow-up (17-, 27-, and 52- weeks), which represents an enhancement over routine care since symptoms of mania will be detected earlier than in usual practice and appropriate treatment referrals made. We will not be asking referrers to withhold any treatment. Participation in assessments may reduce the (frequently high) number of contacts required in order to receive appropriate treatment for BD. Assessments will identify untreated BD and any risks to self or others that require immediate action. TAU alone will not include liaison with a clinical team, should one be involved, except where risk issues necessitate this. This is a pragmatic approach that will improve generalisability of our findings. As in previous trials we have undertaken, there will be a clear safety protocol to alert clinicians should suicidal or dangerous ideation emerge, and an operational protocol for initiating high quality routine care should conversion occur.

Treatment as usual will include standard psychiatric care, psychological and vocational interventions from a variety of agencies will be available to both treatment and control arms (although, in our experience, provision for this population is poor). Due to diagnostic uncertainty, access to services includes Improving Access to Psychological Therapies (IAPT), CAMHS, primary care, EIT and community mental health teams. CBT_{BAR} differs from standard NHS treatment for young people with mood swings as highlighted in our RfPB trial [59]. All routine or additional treatments in both conditions will be monitored using a Treatment Documentation Sheet and specific treatments (anti-depressant and psychotherapy treatment) monitored within the LIFE assessment tool as important potential confounders.

CONCOMITANT THERAPY

It would be unethical to restrict the therapeutic options of the young people participating. Our approach will, therefore, be primarily to record the use of all other medication and psychological therapies, document details of dosage, and ensure the follow-up of all randomised participants, irrespective of the interventions that they subsequently receive.

We will collect participant self-report on the use of medication and psychological therapies (including CBT or CBT informed treatments). All participants will be eligible to receive medications (other than mood stabilisers for longer than 6-weeks or antipsychotics for longer than 3-weeks at baseline) as well as psychological interventions.

ASSESSMENT OF ADHERENCE TO TREATMENT

Four related aspects will be monitored and assessed: (i) participants' adherence to the therapy; (ii) therapist competence (iii) therapist adherence to the manual (iv) overall therapy fidelity. Participants' adherence to the therapy will be assessed by recording the number of sessions offered and attended, including length of sessions attended, and completion of between-sessions tasks (therapy 'homeworks').

Therapist competence and adherence to the manual will be monitored through recordings of therapy sessions, with participants' consent. This is a widely accepted approach to the standardisation of psychological therapies. Therapists will have weekly supervision from a senior clinical psychologist from the central team, who will listen

to and provide detailed feedback on a selection of therapy tapes, with participants' consent, on a weekly basis, to ensure competence and adherence. All therapists and supervisors will also meet remotely with the research team therapy leads for monthly group supervision. This will be done throughout the therapy delivery period to provide quality assurance and ensure action can be taken if required.

Therapy tapes from five participants on each site (total of 25 participants) will be randomly chosen, with participants' consent, to be rated by a clinician independent from the trial, to provide an objective verification of therapist competence and adherence to the manual. Therapist competence will be rated using an existing measure assessing skills and competences related to delivering CBT [93] in line with national programmes and treatment trials utilising CBT models. A rating form for therapist adherence to the manual will be utilised and will consist of a list of therapeutic procedures extracted from the CBT_{BAR} treatment protocol.

To assess overall therapy fidelity, following each session, therapists will complete a checklist to record content of sessions in terms of agenda targets, homework tasks and change strategies used. These data will be extracted at regular time points throughout the trial to check therapy milestones are being met and ensure the therapy protocol is being followed. This ongoing monitoring will pick up on any fidelity issues across sites or individual therapists and will inform training and supervision content.

STUDY PARTICIPANT SUPPORT

We will attempt to ensure that treatment as usual conforms to ethical practice and is standardised to some extent by the provision of 3 additional components – ensuring registration with a GP, a suicide risk management plan where relevant and a crisis card for participants. Crisis cards will include helplines which may be national or local numbers (specific for each site) useful for this group. All participants will be offered a standardised telephone contact within 48 hours of assessments. Participants will not be denied any existing service in either arm of the trial. In both arms, they will be encouraged to engage in and continue with existing treatments. Standard psychiatric care, psychological and vocational interventions from a variety of agencies will also be available to both treatment and control arms (although, in our experience, provision for this population is poor). All study participants will be provided with contact details for the researchers and principal investigator of the study so the potential participant can contact research staff to ask any questions or discuss any concerns they might have about their participation.

7. (Serious) Adverse Events

For the purpose of recording and reporting (Serious) Adverse Events for this trial, the GMMH (sponsor) Standard Operating Procedure (RD2OP41 Recording and Reporting Adverse Events for non-CTIMPS) will be followed.

DEFINITION OF ADVERSE EVENTS (AE's)

Any untoward medical or psychological occurrence in a patient or trial participant receiving psychological therapy or other trial intervention and which does not necessarily have a causal relationship with this intervention. An adverse event can therefore be any unfavourable and unintended sign, symptom, or disease in any subject in a trial (including those in an untreated control group), whether considered related to the investigational psychological therapy/intervention.

As well as broadly defined 'medical events' including self-harm and worsening of symptoms which were absent or present at baseline, adverse event recording will also include capturing information about the occurrence of non-medical events such as arrest, imprisonment, and violence to others, which may be contributing factors to an AE or may indicate that an AE has occurred. As an example of the latter, a participant's increased drug abuse—an AE—could result in an arrest.

DEFINITION OF SERIOUS ADVERSE EVENTS (SAE's)

Any untoward medical or psychological occurrence that:

- Results in death
- Is life-threatening (NOTE: this refers to an event in which the subject was at risk of death at the time of event; it does not refer to an event which hypothetically might have caused death if it were more severe)
- Requires inpatient hospitalisation or prolongation of existing hospitalisation (We plan to scrutinise any instances of patients being admitted to psychiatric hospital in the period of the therapy. These events are likely to come to the attention of the therapists or assessors)
- Results in persistent or significant disability / incapacity
- Other 'important medical events' may also be considered serious if they jeopardise the participant or require an intervention to prevent one of the above consequences plus any serious violent incidents or formal complaints about the intervention.

NB: Planned hospitalisation for a pre-existing condition, without a serious deterioration in health, is not considered a serious adverse event.

REPORTING PROCEDURES FOR ADVERSE EVENTS

For the avoidance of doubt, all AE/SAEs should be collected for all trial subjects from the time of their enrolment into the study. The time of enrolment is defined as the time at which, following recruitment, a subject sign and dates the informed consent form. Initially all adverse events should be recorded on the Adverse Events Report Form by whoever has identified the event. This form should then be shared with the Chief Investigator ([name]) or trial manager ([name]) who makes an assessment as to whether the event is defined as serious in consultation with both the definitions in the Protocol and the GMMH SOP (RD2OP41 Recording and Reporting Adverse Events for non-CTIMPS). The response to an adverse incident will be determined on a case-by-case basis and in line with HRA guidance. The recorded AE's will be regularly monitored by the trial management group in line with Good Clinical Practice Guidelines.

REPORTING PROCEDURES FOR SERIOUS ADVERSE EVENTS

A serious adverse event (SAE) occurring to a participant will be reported to the following agencies and committees using the HRA report of serious adverse event form (see HRA website):

- To the sponsor, no later than 3 calendar days from awareness of the event at the site.
- The REC that gave a favourable opinion of the study The DMC who will be responsible for reviewing serious, unexpected and related events
- Additionally, all SAE's will be reported to the responsible clinical team and the TSC.
- Finally, details of all serious and non-serious adverse events will be reported externally to the funder in regular progress reports.

